10.1.3 Serious adverse events

Of all the unfavorable medical events that developed with administration of drugs (irrespective of dose), serious adverse event is an event that:

1. Results in death during protocol treatment* and all deaths irrespective of a causal relationship with protocol treatment.

*: Period from initiation of protocol treatment up to 4 weeks (28 days) after discontinuation of protocol treatment or initiation of follow-up treatment.

2. Results in death after discontinuation** of protocol treatment for which a causal relationship with protocol treatment cannot be denied. However, death obviously due to the underlying disease is not applicable.

**: from 29 days after discontinuation of protocol treatment or from initiation of follow-up treatment

3. Is life-threatening. The term “life-threatening” refers to an event in which the subject was at risk of death during onset of the adverse event; it does not refer to an event which hypothetically might have caused death if it were severer.

4. Requiring hospitalization or prolongation of hospitalization

However, hospitalization or prolongation of hospitalization for the following reasons will not be handled as a serious adverse event.

- (1) Preplanned inpatient hospitalization or prolongation of existing hospitalization

CONFIDENTIAL

- (2) Inpatient hospitalization or prolongation of existing hospitalization unrelated to an adverse event
5. Results in persistent or significant disability/incapacity.
6. Leads to a congenital anomaly/birth defect.
7. Other medically significant condition: medically important event which causes a risk to a subject even if it is not immediately life-threatening, nor does it result in death or hospitalization, or requires an action or treatment to prevent the results shown in 1 to 6 above.

10.1.4 Special interest adverse event for sponsor

Adverse events listed in Table 10.a “Takeda Medically Significant AE List” will be handled as “special interest adverse event” for sponsor irrespective of severity determined by the investigator or the subinvestigator. Further, any adverse events listed in Table 10.a that has been determined as serious by the investigator or the subinvestigator will be handled as serious adverse event.

Table 10.a Takeda Medically Significant AE List

Acute respiratory failure/acute respiratory distress syndrome (ARDS)	Hepatic necrosis
Torsades de pointes/ ventricular fibrillation/ventricular tachycardia	Acute hepatic failure
Malignant hypertension	Anaphylactic shock
Convulsive seizure (including convulsion and epilepsy)	Acute renal failure
Agranulocytosis	Pulmonary hypertension
Aplastic anemia	Pulmonary fibrosis (including interstitial pneumonia)
Toxic epidermal necrolysis/ oculomucocutaneous syndrome (Stevens-Johnson syndrome)	Neuroleptic malignant syndrome/ malignant hyperpyrexia
	Spontaneous abortion/ stillbirth and fetal death
	Confirmed or suspected transmission of infection by a medicinal product
	Confirmed or suspected endotoxin shock

10.1.5 Severity of adverse events

The severity of adverse event is classified into 5 grades (Grade 1-5) as follows based on the Common Terminology Criteria for Adverse Events (hereafter referred to as CTCAE, Japanese edition JCOG version 4.03), of the National Cancer Institute, USA. Furthermore, the grade for adverse events not listed in CTCAE will be classified according to the following criteria.

Table 10.b CTCAE (Japanese edition JCOG version 4.03) Grade

Grade 1	Mild; asymptomatic or slightly symptomatic; only clinical or test findings; or requiring no treatment
Grade 2	Moderate; requiring the least treatment or local or non-invasive treatment; or interfering with age-appropriate activities of daily living except for self-care activities*
Grade 3	Severe or medically critical, but not immediately life-threatening; requiring hospitalization or prolongation of existing hospitalization; disabling/incapacitating; or interfering with self-care activities of daily living**
Grade 4	Life-threatening; or requiring emergent treatment
Grade 5	Death due to an adverse event

AE: Adverse Event, “;” stands for “or”

*: Activities of daily living except for self-care activities include meal preparation, shopping for daily necessities and clothings, phone call, and financial management.

**: Self-care activities of daily living include bathing, dressing, eating, toilet, and oral drug intake, and indicate that a person is not confined to bed.

10.1.6 Causality of adverse events

Causal relationship between protocol treatment (panitumumab + TAS-102 combination therapy) and adverse events, and causal relationship between panitumumab and adverse events (information on causal relationship with panitumumab will be collected only when causal relationship is “related” with protocol treatment) is classified and defined as described below. Information on causal relationship with adverse event is not collected for any drugs other than protocol treatment.

Related	An adverse event with apparent temporal relation (including clinical course after discontinuation). Possibly due to protocol treatment or panitumumab although other factors such as underlying disease, complications, concomitant drugs/treatment are also presumed.
Not related	An adverse event with no chronological correlative relationship with protocol treatment (chemotherapy, panitumumab, or bevacizumab). Very likely due to other factors such as underlying disease, complications, and concomitant drugs/treatment.

CONFIDENTIAL

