6.0 CLINICAL STUDY DESIGN

6.1 Clinical study design

This phase I/II study is a multi-center, open-label single-arm study that consists of a phase I part (dose de-escalation) which will assess the tolerability and RD of Panitumumab in combination with TAS-102 as primary objective, and a phase II part which will assess the efficacy and safety of Panitumumab in combination with TAS-102 as primary objective in patients with RAS wild-type unresectable, advanced/recurrent colorectal cancer. In the phase I part, the subjects will be included sequentially into Cohort 1 and 2, 3 subjects each with the same dosage and administration. In the phase II part, 46 subjects will be included additionally for RD confirmed in the phase I part.

[figure not shown]

Figure 6.a Outline of study design

In the phase I part, each cohort will be conducted with 3 subjects, the sponsor will assess tolerability of the dosage and administration based on the incidence of Dose Limiting Toxicity (hereinafter referred to as DLT) during the assessment period and determine whether or not to move on to the next cohort (opinion from the Data Monitoring Committee [hereinafter referred to as DMC] will be confirmed appropriately upon determination). Therefore, in Cohort 1, if occurrence of DLT is ≤ 2 subjects out of 3, the dosage and administration will be determined tolerable and will move on to Cohort 2. However, if DLT is observed in 2 subjects during DLT assessment period in Cohort 1, subjects will be included one at a time in Cohort 2 in consideration for safety to assess DLT.

CONFIDENTIAL

Similarly 3 subjects will be included in Cohort 2 and DLT will be assessed in a total of 6 subjects of Cohort 1 and 2 at most. If DLT is observed in 3 subjects included in Cohort 1, or DLT is observed in 3 subjects from a total of 6 subjects of Cohort 1 and 2, the sponsor will promptly request to postpone new enrollment of subjects to each site and after consultation with the Research Steering Committee and DMC on the continuation of the study, will determine whether or not to continue the study.

If study is to be continued, taking in account of the adverse event that occurred, either panitumumab or TAS-102 or both drugs will be reduced one step and re-conducting the phase I part similarly will be considered. If DLT is observed in 3 subjects after reducing 1 step of panitumumab or TAS-102 or both drugs, the study will be discontinued.

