7.1 Inclusion criteria at enrollment

Patient's eligibility will be determined based on the following criteria.

1. In the opinion of the investigator* or the subinvestigator, the patient is capable of understanding and complying with protocol requirements.

*: A personnel taking part in conducting the study and presides over the study related activities within the belonging study site.

2. Patients who signs and dates a written ICF prior to the initiation of any study procedures
3. Patients aged ≥ 20 to < 75 years at the time of informed consent
4. Patients with unresectable adenocarcinoma originating in the large intestine (excluding carcinoma of the appendix and anal canal cancer)
5. Patients who have measurable lesion (refer to Appendix A) according to Response Evaluation Criteria in Solid Tumors (hereinafter referred to as RECIST) ver 1.1
6. Patients with colorectal cancer refractory or intolerant* to chemotherapy including fluopyrimidines, oxaliplatin (OXA), irinotecan (IRI) and angiogenesis inhibitors (bevacizumab, afibbercept, ramycirumab, etc.)

*: Refractory or intolerant if applicable to any of the following

- 1) If recurrence is observed during supportive chemotherapy before or after surgery or from imaging diagnosis within 6 months of completion.
- 2) If imaging or clinical progression is observed during or within 3 months from the last administration of chemotherapy for advanced cancer
- 3) When it is determined that resumption is not possible due to intolerable adverse event toxicities (serious allergic reaction, accumulative neuropathy, etc.)

7. Patients classified as *KRAS/NRAS* wild-type** by *KRAS/NRAS* testing*.

*: *KRAS/NRAS* test will be performed using the in vitro diagnostic that has been approved for marketing.

**: All codons listed below are required to be wild-type. If any codon is unmeasured or unmeasurable, it will not be defined as wild-type.

KRAS	EXON	2	3	4
	codon	12, 13	59, 61	117, 146
NRAS	EXON	2	3	4
	codon	12, 13	59, 61	117, 146

CONFIDENTIAL

8. Patients who may receive oral administration
9. Patients who satisfy the following criteria for the major organ function in tests performed within two weeks (14 days) prior to enrollment.
 - (1) Neutrophil count $1.5 \times 10^3/\text{L}$
 - (2) Platelet count $10.0 \times 10^4/\text{L}$
 - (3) Hemoglobin 8.0 g/dL
 - (4) Total blood bilirubin 1.5 mg/dL
 - (5) AST 100 IU/L (200 IU/L if liver metastases are present)

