10.2.1.2 Reporting of adverse events

At each visit of subject, the investigator or the subinvestigator should confirm whether the onset of subjective symptoms is present or not. Onset of any adverse event that developed after the previous visit should be checked by asking a question such as “how has your condition been since the last visit?” to a subject.

The investigator or the subinvestigator should follow up all subjects who developed adverse events irrespective of a causal relationship with protocol treatment until disappearance of symptoms or abnormal laboratory values, return of clinically problematic abnormal laboratory values to the value before administration of study drug, or if not, until observed changes can be sufficiently explained for other events (persistent/irreversible adverse event, etc.).

All adverse events should be entered into the CRF. The name of the adverse event, date of onset, severity, seriousness, causal relationship with protocol treatment (unrelated or related), further if event has causal relationship “related” to protocol treatment, causal relationship with panitumumab (unrelated or related) should be recorded. Also, for the last course, action taken and outcome concerning protocol treatment as well as date of resolution should be recorded.

Follow-up period of adverse events is until recovery of an adverse event, or the investigator or the subinvestigator judges that further follow-up would be unnecessary.

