12.1 Case report form

The investigator or the subinvestigator should prepare the case report form (CRF) for all subjects who have given consent.

The sponsor or its designee should provide study sites with access authorization to the electronic data capture (hereinafter referred to as EDC). The sponsor should provide the investigator, subinvestigators, and study collaborators with training for utilization of EDC. The CRF will be used to report the information collected during the study period to the sponsor. The CRF will be prepared in Japanese. Data will be directly entered in preparing the CRF.

A change or correction of the CRF will be recorded as an audit trail that records the information before and after the change or correction, the person who made the change or correction, date of change or correction, and its reason.

The investigator or its designee should ensure the accuracy and completeness of the CRF, and provide an electronic signature on the relevant page of the case report form. The investigator bear full responsibility for the accuracy and reliability of all the data entered into the CRF.

The data below will be directly recorded into the CRF.

- Seriousness, severity and causal relationship of adverse event with protocol treatment and “panitumumab”

When the investigator or the subinvestigator makes a change or correction in the data entered into the CRF after fixation of clinical data base, a record (Data Clarification Form) of change or correction in the CRF provided by the sponsor should be used. The investigator should confirm that the record of change or correction in the CRF is accurate and complete, and sign or write name/ affix a seal, and date it.

The sponsor or its designee should confirm CRF has been prepared appropriately. The sponsor or its designee should have access to the medical records of study subjects and in-house records to ensure the accuracy of the CRF as necessary. The completed CRF is the property of the sponsor, and the investigator or the subinvestigator should not disclose the information to a third party without a written permission from the sponsor.

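### Relatedness is recorded for the regimen and for panitumumab but not for TAS-102, so panitumumab-only and both-drug events share one code; the Not related definition also names bevacizumab, which is not given

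*Protocol*

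**What the plan says.** Protocol 10.1.6 opens by setting up two judgements: "Causal relationship between protocol treatment (panitumumab + TAS-102 combination therapy) and adverse events, and causal relationship between panitumumab and adverse events". The second depends on the first, since "information on causal relationship with panitumumab will be collected only when causal relationship is" related for the regimen. The same paragraph then closes the list to drugs outside the regimen: "Information on causal relationship with adverse event is not collected for any drugs other than protocol treatment". Section 10.2.1.2 carries this into reporting: after the regimen judgement, "causal relationship with panitumumab (unrelated or related) should be recorded". Section 12.1 lists the causality data entered directly in the CRF in the same way: "Seriousness, severity and causal relationship of adverse event with protocol treatment and" panitumumab. None of these places has an item for TAS-102.

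The analysis follows the same two fields. The related-event tables in protocol 13.3.4.1 and in SAP version 4.0, 6.3.3 and 7.2.5, exist for protocol treatment and for panitumumab. The DLT listing in SAP 6.3.2 shows the same two causality columns.

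The table in 10.1.6 then defines the Not related category as "An adverse event with no chronological correlative relationship with protocol treatment (chemotherapy, panitumumab, or bevacizumab"). Section 8.1 defines protocol treatment as panitumumab with TAS-102, and 8.11 prohibits other antibody therapy apart from denosumab.

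**The concern.** The phase II part is described in the study summary as exploring what TAS-102 adds to panitumumab monotherapy. A reader of the safety results will ask the same of toxicity. For events that either drug can cause, the recorded data cannot say whether the investigator thought TAS-102 contributed.

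SAP 4.0 shows that this matters to the analysts. Sections 7.2.3.2 and 7.2.3.3 relate stomatitis to the dose of each drug, and 7.2.6.5 cross-tabulates stomatitis with neutropenia and with dermatitis acneiform. Stomatitis is therefore analysed by drug exposure, but attributed by name to only one of the two drugs. Other records do not fill the gap: 10.1.8 defines only discontinuation of protocol treatment as an action taken, and 9.2.8 records doses by drug without a reason for change.

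The bevacizumab wording is a separate fault. It sits in the definition that investigators apply to every adverse event, and it describes a regimen other than the one given.

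**Working it through.** No sample size or error rate is involved, so there is no planned figure to reproduce. The check has three parts.

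**1. What the two fields can separate.** An event may truly be due to panitumumab (P) or not, and to TAS-102 (T) or not.

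| True pattern | Regimen field | Panitumumab field |
|---|---|---|
| neither | not related | not asked |
| T only | related | not related |
| P only | related | related |
| P and T | related | related |

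Four patterns give three codes. T only is identified by elimination. P only and P with T cannot be separated.

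**2. How wide the gap is.** For a given preferred term, let R be the number of subjects with a regimen-related event and N the number with a panitumumab-related event. The SAP counts a subject once per term. From the planned tables, the number of subjects with a TAS-102-related event lies between R − N (every regimen-related event was judged not related to panitumumab) and R. The width is R − (R − N) = N. The uncertainty therefore equals the number of subjects with a panitumumab-related event of that term.

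Inputs for stomatitis:
- TAS-102: 18/119 = 15.1% (Table 4.d)
- Panitumumab, Japanese phase II study: 12/52 = 23% (Table 4.b)
- Panitumumab, Japanese surveillance: 123/1,254 = 9.8% (Table 4.f)

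Assume that the single-agent panitumumab rates carry over to the 52 subjects planned at the recommended dose:
- Low: 0.098 × 52 = 5.1 subjects
- High: 0.23 × 52 = 12.0 subjects

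Other possible overlaps depend much more on the source. Decreased appetite is 55.5% on TAS-102; on panitumumab it is 2.0% in Table 4.f, against 21% for anorexia in Table 4.b. Fatigue is 52.9% on TAS-102; on panitumumab it is 0.7% in Table 4.f, against 25% for malaise in Table 4.b. The Table 4.b terms are not the same terms, so these two are weak evidence. Neutrophil decrease is 73.1% on TAS-102 (51.3% at Grade 3 or higher, Table 4.d) and 0 on panitumumab in Table 4.f, so N would be near zero and elimination works.

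**3. The definition, side by side.** The first sentence of 10.1.6 and section 8.1 give protocol treatment as panitumumab and TAS-102. The Not related row gives chemotherapy, panitumumab or bevacizumab. One listed drug is not part of treatment, and TAS-102 is covered only if it is read as the chemotherapy.

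**The case against.** The strongest reply is that little is lost. Three of the four patterns are identifiable, protocol 4.2 expects hardly any overlap beyond stomatitis, and panitumumab is the named test product, which explains why only it is singled out. The safety endpoint is the percentage of subjects with adverse events, and all-cause tables are planned; neither needs drug-level causality. In a single-arm study giving both drugs in every course, an investigator's opinion would not establish what TAS-102 contributed. All of this stands, and it keeps the point modest. It does not explain why that opinion is sought for one drug and not for the other.

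Several stronger readings are tempting, but the documents do not support them.

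- *TAS-102 toxicity cannot be attributed at all.* Elimination identifies TAS-102-only events.
- *The sentence limiting causality to protocol treatment shuts TAS-102 out.* TAS-102 is part of protocol treatment; the sentence concerns other drugs. The gap comes from the two items named before it and from 10.2.1.2 and 12.1.
- *The phase I dose-reduction choice depends on this field.* Section 6.1 says "either panitumumab or TAS-102 or both drugs will be reduced one step", taking account of the event that occurred. It cites no relatedness field, and the sponsor first consults the Research Steering Committee and the DMC.
- *Misattribution between the drugs could turn 2 of 6 DLTs into 3 of 6.* Section 8.9.3 attributes a DLT to protocol treatment as a whole, so moving an event between the two drugs changes no count.
- *Carry-over from earlier bevacizumab will inflate the related-event or DLT counts.* Entry does require disease refractory or intolerant to "angiogenesis inhibitors (bevacizumab, afibbercept, ramycirumab, etc".), so prior exposure is expected. But 7.2 requires 14 days since previous chemotherapy and recovery of earlier toxicity to Grade 1 (Grade 2 for sensory neuropathy, haemoglobin excepted). Section 10.1.2 records pre-existing conditions separately, and 8.9.3 excludes events whose link to protocol treatment can clearly be denied. Late-onset events are not fully covered, but nothing in the documents gives them a size.

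**Conclusion.** The point holds in a limited form and should be acted on. Relatedness to TAS-102 is not recorded, and events due to panitumumab alone cannot be told from events due to both drugs. For any event term, the count of subjects with TAS-102-related events is uncertain by exactly the number with panitumumab-related events. For stomatitis that is about 5 to 12 of 52 subjects, if single-agent panitumumab rates apply to the combination; the documents give no combination rate. For haematological toxicity the loss is close to nil. The inference by elimination also assumes that investigators judge the two existing items consistently.

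The Not related wording is a plain error: it contradicts the opening of its own section and section 8.1. Its likely effect on counts is small, since the correct regimen is named just above it, but it belongs to a rule applied to every event. Neither fault touches the primary endpoint, the DLT count or the sample size.

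**What to change.** 1. In protocol 10.1.6, replace the parenthesis in the Not related definition with *(panitumumab or TAS-102)*.
2. In 10.1.6, 10.2.1.2 and 12.1, add a TAS-102 item (related / not related), asked whenever an event is related to protocol treatment, as is done for panitumumab.
3. In the SAP, add TAS-102-related versions of the related-event tables in 6.3.3 and 7.2.5, and add the item to the DLT listing in 6.3.2.

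The cost is one extra yes/no answer per regimen-related event, one wording correction and some repeated tables. No dose rule, endpoint or sample size changes.

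If the item cannot be added, the SAP should say that TAS-102 relatedness is inferred from events related to the regimen and not to panitumumab, tabulate that group, and state that panitumumab-related events may also include a TAS-102 contribution.

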10.1.7 Date of onset of adverse events

The date of onset of adverse events will be determined according to the following criteria.

Adverse event, etc.	Date of onset
Signs, symptoms, and diseases (diagnoses)	The subject, investigator, or subinvestigator will record the date on which the sign or symptom of an adverse event is first noticed.
Asymptomatic diseases	The date on which diagnosis is confirmed by testing will be recorded. Even if testing reveals old findings or if the time of occurrence can generally be estimated, the date on which diagnosis is confirmed will be recorded.
Aggravation of concurrent medical conditions	The subject, investigator, or subinvestigator will record the date on which a disease or aggravation of a disease is first noticed.
Test results that became abnormal after initiation of protocol treatment	The test date on which abnormal test results determined to be clinically problematic were observed will be recorded.
Test results that are abnormal at initiation of protocol treatment and aggravated in later testing	The date on which the time profile of a laboratory value shows a clear increase or decrease, based on medical judgment, will be recorded.

